Clarified that statistical analyses will be performed after all subjects complete Visit 10 and Visit 15 and that the primary efficacy assessment will be at Visit 14, Week 48.

AMENDMENT RATIONALE

Protocol Amendment 3.0 dated 08FEB2019 allows for the concomitant use of narrowband-UVB according to the Standard of Care protocol for the treatment of vitiligo to see if there is a synergistic effect on repigmentation.

ATI-50002 Topical Solution was not a skin sensitizer in a mouse local lymph node assay. ATI-50002 was shown to have the potential to react to light. In a 3T3 cell assay, ATI 50002 in the absence and presence of UVA did not cause toxicity and, therefore, there was no phototoxic potential identified for ATI-50002.

Protocol Changes			
Protocol Version	Date	Section	Revisions
4.0	08FEB2019	5.6 5.6.1	Added: NB-UVB treatments may be administered according to the Standard of Care protocol for the treatment of vitiligo after the subject has completed Visit 9. NB-UVB treatments should be recorded in the source documents and on the Concomitant Therapies Log of the eCRF.

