5.6. Permitted Concomitant Medications, Therapies and Over the Counter Products (OTC)

All topical products used on the face and neck should be reviewed by the investigator or designee and are permitted, if in the opinion of the investigator or designee will not affect the safety or efficacy of the subject during the study. Subjects will be allowed to take medications not restricted by the protocol as long as they have been on a stable dose prior to study entry. Vitamins, minerals, and dietary supplements are permitted during the study, if the subject has been on a stable dose prior to study entry and, in the opinion of the Investigator, will not affect the safety or efficacy of the subject during the study.

Topical therapies such as topical corticosteroids are permitted as long as they are not applied on or near the face and treated areas of the neck. Inhaled or intranasal corticosteroids are allowed in

the study. Male subjects who shave at screening and baseline should maintain the same shaving regimen during the study.

NB-UVB treatments may be administered according to the Standard of Care protocol for the treatment of vitiligo after the subject has completed Visit 9. NB-UVB treatments should be recorded in the source documents and on the Concomitant Therapies Log of the eCRF.

Prior permitted concomitant medications taken within 30 days of beginning treatment with ATI-50002 Topical Solution will be documented in the subject's source document and eCRF. In addition, any new permitted medications administered during protocol treatment and through Week 28 (Visit 11) will be documented in the subject's source document and eCRF.

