8. Quantify the facial vitiligo BSA involvement. The subject must have non-segmental facial vitiligo involving at least 0.25% TBSA (excluding: the area from the eyebrows to and including the upper eyelids, the area from the bony rim of the orbit to and including the lower eyelids; mucosal lip areas; and forehead and chin areas covered by the stereotactic positioning device) with at least one facial area with normal pigmentation.
9. Perform the Facial Vitiligo Area Scoring Index (F-VASI).
10. Perform the total body VASI.
11. Confirm subject is eligible to apply the first dose of study medication.
12. Have the subject perform a pre-application Local Tolerability Assessment (LTA).
13. The Investigator or designee will perform a pre-application LTA.
14. Collect blood samples for clinical laboratory tests.
15. Take standardized photographs.
16. Conduct an ECG.
17. Have the subject complete the VitiQoL.
18. Discharge from the study subjects who are not eligible to apply the first dose of study medication.

For subjects who are eligible to apply the first dose of study medication the investigator or designee will perform the following procedures:

1. Dispense study medication to the subject.
2. An investigational staff member will instruct the subject on the proper study medication application technique and will observe the subject's first study medication application.
3. A staff member will monitor the subject for at least 20 minutes after the first study medication application completion time to detect any adverse events.
4. Have the subject perform a post-application LTA 10 (± 4) minutes after the application completion time.
5. The investigator or designee will perform a post-application LTA 20 (± 4) minutes after the application completion time.
6. Review the study instructions with the subject.
7. Schedule Visit 3 as appropriate.

6.4.3. Visit 3-9 (Weeks 1, 2, 4, 8, 12, 16 and 20) These visits must occur on the following weeks after Visit 2:

- Visit 3, 1 week (± 4 days)
- Visit 4, 2 weeks (± 4 days)
- Visit 5, 4 weeks (± 4 days)
- Visit 6, 8 weeks (± 4 days)
- Visit 7, 12 weeks (± 4 days)
- Visit 8, 16 weeks (± 4 days)
- Visit 9, 20 weeks (± 4 days).

At these visits, the investigator or designee will perform the following procedures:

1. Query the subject in a non-directive manner about any changes in her/his health since the previous visit and report all AEs on the appropriate form.

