6.4.4. Visit 10 (Week 24)

This visit must occur 24 weeks (± 4 days) after Visit 2.

At this visit, the investigator or designee will perform the following procedures:

1. Query the subject in a non-directive manner about any changes in her/his health since the previous visit and report all AEs on the appropriate form.
2. Query the subject about any changes in her/his concomitant therapies since the previous visit and report changes on the appropriate form.
3. Confirm the subject continues to comply with all study restrictions and has followed all study instructions.

4. Measure vital signs.
5. Conduct an ECG.
6. Collect blood samples for clinical laboratory tests.
7. Perform a urine pregnancy test for WOCBP.
8. Have the subject perform an LTA.
9. The investigator will perform an LTA.
10. Perform the F-VASI.
11. Perform the total body VASI.
12. Have the subject complete the VNS.
13. Have the subject complete the SVSS.
14. Have the subject complete the VitiQoL.
15. Collect all study medication.
16. Take standardized photographs.
17. Review the study instructions with the subject.
18. For subjects who agree to continue to participate in additional study visits (Visits 12-15):
 - a. Obtain consent for additional study visits, Visit 12-15:
 - b. Dispense study medication.
 - c. Review study instructions with the subject.
19. Schedule Visit 12. For subjects who do not consent to continue with additional study visits (Visit 12-15), schedule the next visit, Visit 11.

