7.6. Dose Modification

If the subject experiences application site AE(s), study medication may be stopped for up to a total of 3 days or the frequency of study medication application may be reduced from twice-daily to once-daily for up to a total of 6 days. Dose interruptions must be documented in the source document and eCRF. Dose modifications greater than these must be reviewed and approved by the Medical Monitor. Refer to Section 9.2.4 for Study Medication Interruption or Discontinuation due to related SAEs or specific abnormal laboratory values.

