8.2.5. Local Tolerability Assessment (LTA)

The LTA is the investigator's assessment of the average overall severity of signs and the subject's assessment of the average overall severity of symptoms associated with an application site reaction on the treated areas of the face. The investigator and subject must NOT refer to any other evaluation to assist with these assessments. This is not a comparison with the assessment at any other time point.

At Visits 2-11, the investigator and the subject will evaluate the LTA signs and the LTA symptoms respectively.

LTA Signs (Investigator or designee assessment):

- Erythema
- Edema
- Scaling/dryness

LTA symptoms (Subject assessment):

- Stinging
- Burning

The investigator will assess the LTA signs as follows:

- At Visit 2:
 - Prior to the first study medication application
 - 20 (± 4) minutes after the application completion time.
- At Visits 3-11.

The subject will assess the LTA symptoms as follows:

- At Visit 2:
 - Prior to the first study medication application report the LTA for each symptom over the previous 24 hours
 - 10 (± 4) minutes after the application completion time report the average severity since the application completion time.
- At Visits 3-11:
 - Report the average LTA for each symptom over the previous 24 hours.

The investigator, for the signs, should report the one integer that best describes the average overall severity on the treatment areas of the face using the scales below:

Local Tolerability Assessment – Erythema

Grade	Descriptor
0	Clear: No erythema present
1	Mild: Slight erythema
2	Moderate: Definite erythema
3	Severe: Marked, fiery erythema

Local Tolerability Assessment – Edema

Grade	Descriptor
0	Clear: No edema present
1	Mild: Slight edema
2	Moderate: Definite edema
3	Severe: Marked edema

Local Tolerability Assessment – Dryness/Scaling

Grade	Descriptor
0	Clear: No signs of dryness or scaling
1	Mild: Slight roughness (may be more easily felt than seen), barely perceptible scaling
2	Moderate: Moderate roughness, definite scaling
3	Severe: Marked roughness, heavy scaling

The subject, for the symptoms, should report the one integer that best describes the average overall severity on the treatment areas of the face using the scales below:

Local Tolerability Assessment – Itching

Grade	Descriptor
0	Clear: No itching
1	Mild: Slight itching, not bothersome

2	Moderate: Definite itching, slightly bothersome
3	Severe: Intense itching, bothersome and/or uncomfortable

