9.1.6. Relationship to study medication

The investigator will determine if there is a reasonable causal relationship between the study medication and an AE or not. The investigator will use her/his best medical judgment and consider all relevant factors (e.g., temporal relationship, location of the event, the subject's relevant medical history, concomitant therapies and concurrent conditions) to determine the relationship of the AE to the study medication. The investigator will define the relationship of an AE to the study medication by selecting one of the following categories:

Related – There is a reasonable causal relationship between the study medication and the AE.

Not Related – There is not a reasonable causal relationship between the study medication and the AE.

The expression “reasonable causal relationship” is meant to convey in general that there are facts (evidence) or arguments to suggest a causal relationship (International Conference on Harmonization [ICH] E2A).

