11.2. Statistical Methods

Summary descriptive statistics (N, mean, median, SD) by visit will be provided for all safety and efficacy parameters. Primary and secondary efficacy parameters are described below:

Primary Efficacy Parameter

Mean change from baseline in facial depigmentation in the AOI will be quantified using Canfield-2-D photographic image analysis from baseline (Visit 2) compared to Week 48 (Visit 14).

Secondary Efficacy Parameters:

Mean change from baseline in facial depigmentation will be calculated as the mean change in Facial assessment of the Vitiligo Area Scoring Index (F-VASI) from Visit 2 compared to Week 24 (Visit 10) and if applicable, Week 48 (Visit 14). F-VASI is a modification of the validated quantitative assessment scale for vitiligo which evaluates the percentage of vitiligo involvement of the face only.

Mean change from baseline in facial depigmentation in the AOI based on Canfield 2-D Photographic analysis from Visit 2 compared to Weeks 4, 8, 12, 16, 20, 24, 32, 40, and post-treatment Week 52 (Visits 5-11, and 12, 13, and 15).

Mean change from baseline in the Facial assessment of the Vitiligo Area Scoring Index (F-VASI) from Visit 2 compared to Weeks 4, 8, 12, 16, 20, 24, 32, 40, 48 and post-treatment Week 52 (Visits 5-11, and Visits 12, 13, 14 and 15).

Mean change from baseline in the VitiQoL from Visit 2 compared to Week 12, 16, 20, 24, and 48 (Visits 7-10, 14).

Treatment success based on the subject's assessment of vitiligo on the Vitiligo Noticeability Scale (VNS) at Week 4, 8, 12, 16, 20, 24, 32, 40, and 48.

Mean change from baseline in total VASI from Visit 2 to Visits 7 and Visit 14 (Week 48) will be assessed for descriptive purposes only to track disease progression in untreated areas.

Safety analyses will include descriptive statistics calculated on the safety parameters using the safety population. The proportion of subjects with treatment-emergent adverse events will be tabulated and presented by Medical Dictionary for Regulatory Activities (MedDRA) System Organ Class. Vital signs and clinically relevant abnormal laboratory results will also be tabulated and presented. Change from baseline in the Local Tolerability Assessments (LTA) to end of treatment (Visit 10) will be summarized.

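### Section 11.2 does not separate the Visit 10 local tolerability result, or later skin adverse events, by NB-UVB use, although NB-UVB is permitted once Visit 9 is complete

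*Combined protocol and SAP*

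**What the plan says.** Safety and tolerability are part of the primary objective (Section 4.1).

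The Amendment Rationale introduces NB-UVB to look for synergy on repigmentation, and its table of changes lists only Sections 5.6 and 5.6.1. Section 5.6 reads: "NB-UVB treatments may be administered according to the Standard of Care protocol for the treatment of vitiligo after the subject has completed Visit 9". No body site is named or excluded. Sessions are to be recorded in the source documents and on the Concomitant Therapies Log.

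On LTA collection, Section 8.2.5 says: "At Visits 2-11, the investigator and the subject will evaluate the LTA signs and the LTA symptoms respectively". The schedule for Visits 12 to 15 has no LTA row. Section 6.4.5 has Visit 11 marked as not done for subjects who agree at Visit 10 to continue.

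On analysis, Section 11.2 promises by-visit descriptive statistics for all safety parameters and then singles out one tolerability result: "Change from baseline in the Local Tolerability Assessments (LTA) to end of treatment (Visit 10) will be summarized". Treatment-emergent adverse events are tabulated over all treated subjects, overall and by System Organ Class. Neither summary refers to NB-UVB.

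**The concern.** The one LTA result that the plan names falls at the first LTA visit that permitted NB-UVB can affect. LTA grades erythema, edema, scaling or dryness and burning or stinging on the treated face. Light therapy to the same skin could plausibly move several of these grades. The documents do not discuss this overlap, so it is an assumption here. So is facial exposure, although the aim of synergy in a facial vitiligo study makes it the natural reading.

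If the plan is followed as written, the Visit 10 change from baseline describes drug alone in some subjects and drug plus NB-UVB in others, in unstated proportions. Skin events that start after Visit 9 are mixed in the same way. At stake is a clean statement of how well the drug alone is tolerated, and a view of skin reactions in those who received both.

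**Working it through.** The plan gives no figure to reproduce: Section 11.1 states that no formal power calculation was done.

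**Inputs.** Visit 9 is Day 141 ± 4, Visit 10 is Day 169 ± 4 and Visit 14 is Day 337 (Section 6.3). Section 6.4.4 confirms the Visit 10 window: "This visit must occur 24 weeks (± 4 days) after Visit 2". Planned enrolment is 33 (Section 11.1). The number of NB-UVB users and all reaction rates are assumptions.

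**1. Gap before the Visit 10 LTA.**
- Nominal: 169 − 141 = 28 days.
- Shortest: (169 − 4) − (141 + 4) = 20 days.
- Longest: (169 + 4) − (141 − 4) = 36 days.

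**2. Which LTA visits can be affected.**
- Visits 2 to 9 precede any permitted NB-UVB.
- Visit 10 can follow NB-UVB while the subject is on study drug.
- Visit 11 is done only in subjects who were not re-supplied with drug at Visit 10, so it is an off-drug reading.
- Visits 12 to 15 have no LTA.

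Visit 10 is therefore the only scheduled on-drug LTA that can follow NB-UVB. Adverse events remain exposed for longer: Visit 9 to Visit 14 is 337 − 141 = 196 days.

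**3. Who can be affected at Visit 10.** Enrolment dates are not given. Amendment 3 is dated 08FEB2019, and Visit 10 is 168 days after baseline. Only subjects with a baseline after about 24AUG2018 have a nominal Visit 10 after that date. The Amendment History says that a letter of 05OCT2018 raised enrolment from 24 to 33. If those 9 extra subjects entered after the letter (an assumption), their nominal Visit 9 would fall on or after 22FEB2019 (05OCT2018 plus 140 days), which is after the amendment date.

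**4. Effect on the Visit 10 LTA mean.** Suppose NB-UVB adds 1 grade in k users and nothing in the others. The overall mean rises by k/33:
- k = 3: 0.09 grade
- k = 8: 0.24 grade
- k = 16: 0.48 grade

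**5. Effect on a local adverse event rate.** Assume 10% on drug alone and a rate q of 30% to 50% in users. Overall rate = [(33 − k) × 0.10 + k × q]/33:
- k = 3: 11.8% to 13.6%
- k = 8: 14.8% to 19.7%
- k = 16: 19.7% to 29.4%

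**6. What the unsplit figure leaves open.** With 7 of 33 subjects reporting a local event and 16 users, the rate among the 17 non-users could lie anywhere from 0/17 = 0% to 7/17 = 41%.

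**7. What a split could show.** With zero events in n subjects, the exact one-sided 95% upper bound is 1 − 0.05^(1/n): 8.7% for n = 33, 17.1% for n = 16, 31.2% for n = 8 and 63.2% for n = 3.

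**The case against.** The strongest reply is that most of what is needed already exists. Section 11.2 gives by-visit summaries of all safety parameters, so LTA at Visit 9 will be tabulated. NB-UVB goes on the Concomitant Therapies Log. Section 9.1.6 tells the investigator to weigh timing, location and concomitant therapies when rating causality. The adverse event tables count events and do not assign them to the drug. The study is a small, open-label, descriptive pilot. All of this stands, and it limits the point to how the results are presented. It does not supply the separation: the named LTA result is still Visit 10, and no table by NB-UVB use is planned.

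A reader might infer three stronger things that the documents do not support.

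- **That drug and light reactions can never be told apart.** The log and the pre-Visit 10 LTA data allow before/after and user/non-user summaries. They are simply not prespecified.
- **That NB-UVB was allowed because of the UVA assay.** The Amendment Rationale does report that "ATI 50002 in the absence and presence of UVA did not cause toxicity and, therefore, there was no phototoxic potential identified", but it does not call this the justification, and the sentence itself names UVA as the condition tested. Other photosafety data may exist outside these documents.
- **That the two-way causality rating hides combination reactions.** It is rated against study medication only, but concomitant therapies must be considered, and another category would not change the tables at issue.

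**Conclusion.** The point holds as a gap in the planned analysis. Permitted NB-UVB can precede the named tolerability assessment by about 3 to 5 weeks, and neither the Visit 10 LTA result nor the adverse event tables separate subjects or periods by exposure.

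The size cannot be stated from the documents because the number of users before Visit 10 is not given. It is zero at Visit 10 for anyone who passed that visit before Amendment 3 took effect, a situation that the schedule footnotes anticipate. The figures above show how the mixing scales under stated assumptions and are not estimates. For LTA the problem is confined to Visit 10 and, off drug, Visit 11. For adverse events it runs from Visit 9 to the end of follow-up.

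A reader might expect a split to reveal a drug-light interaction. It cannot: no group receives NB-UVB without study drug, so a UVB effect and an interaction stay confounded. What the split does deliver is a tolerability result free of NB-UVB and a visible count of skin events in those who had both.

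**What to change.** In Section 11.2, with matching text in the synopsis:

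1. Present LTA change from baseline to Visit 9, already produced by visit, as the NB-UVB-free tolerability result for all subjects. Show LTA at Visit 10, and at Visit 11 where done, separately for subjects with and without NB-UVB since Visit 9. Label Visit 11 as off treatment. This keeps the Visit 10 data of non-users in view.
2. Tabulate application-site and skin adverse events by onset before or after the first NB-UVB session, and for subjects who never used it, with the follow-up time in each category.
3. Reconcile the description of Visit 10 as the end of treatment with treatment for up to 48 weeks. Visit 10 is the end of treatment only for subjects who do not continue, and LTA is not scheduled at Visit 14.

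Item 2 assumes that the Concomitant Therapies Log holds session dates. Section 5.5 runs concomitant therapies to Week 52, whereas Section 5.6 documents new permitted medications only to Week 28. The two should be aligned so that later NB-UVB dates are captured.

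The cost is wording and table shells, with no new visits or procedures. The downside is imprecision: the exposed group is likely to be small, and with 8 users and no events the upper bound is still 31.2%. The split should be reported as descriptive.

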Mean change from baseline in total VASI from baseline (Visit 2) to Week 4, 8, 12, 16, 20 24 and 48 (Visits 5-15) will be assessed for descriptive purposes only to track disease progression in untreated areas.

Safety analyses will include descriptive statistics calculated on the safety parameters using the safety population. The proportion of subjects with treatment-emergent adverse events will be tabulated and presented by treatment and Medical Dictionary for Regulatory Activities (MedDRA) System Organ Class. Vital signs and clinically relevant abnormal laboratory results will also be tabulated and presented. Change from baseline (Visit 2) in the Local Tolerability Assessments (LTA) to end of treatment (Visit 10) will be summarized.

Data from all enrolled and treated subjects will be presented and summarized. Safety summaries will include listings by study medication of adverse events incidences within each MedDRA System Organ Class, and changes from pre-application values in vital signs. Adverse event summaries will be presented showing the proportion of subjects experiencing adverse events, both overall and by MedDRA System Organ Class.

TABLE OF CONTENTS

1. SYNOPSIS	6
2. INTRODUCTION.....	18
2.1. Summary.....	18
3. STUDY RATIONALE.....	20
3.1. Study Rationale.....	20
4. STUDY OBJECTIVES	20
4.1. Primary Objective	20
4.2. Secondary Objectives	20
5. SELECTION AND DISPOSITION OF STUDY POPULATION	20
5.1. Number of Subjects and Study Sites	20
5.2. Study Population Characteristics.....	20
5.3. Inclusion Criteria.....	21
5.4. Exclusion Criteria.....	21
5.5. Previous and Concomitant Medications and Therapies.....	23
5.6. Permitted Concomitant Medications, Therapies and Over the Counter Products (OTC)	23
5.6.1. Prohibited and/ or Restricted Medications	24
5.7. Subject Identifier (SI)	24
5.8. Replacement Subjects	25
5.9. Subject Withdrawal Criteria	25
5.10. Study Termination	25
6. INVESTIGATIONAL PLAN.....	26
6.1. Overall Study Design.....	26
6.2. STUDY PROCEDURES	26
6.3. Schedule of Assessments	27
6.4. Study Visits Description and Procedures	30
6.4.1. Visit 1/ Screening (Day -28 to 0)	30
6.4.2. Visit 2 (Day 1) / Baseline.....	30
6.4.3. Visit 3-9 (Weeks 1, 2, 4, 8, 12, 16 and 20) These visits must occur on the following weeks after Visit 2:	32
6.4.4. Visit 10 (Week 24).....	32
6.4.5. Visit 11 (Week 28).....	33
6.4.6. Visit 12 (Week 32).....	34

6.4.7. Visit 13 (Week 40).....	34
6.4.8. Visit 14 (Week 48).....	35
6.4.9. Visit 15 (Week 52).....	35

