2. You will be asked to apply a thin layer of study medication to the white areas of your face and if applicable, your neck including $\frac{1}{2}$ inch around the white areas (excluding your eyelids and red (mucosal) lip areas) with an applicator as instructed by the study doctor or the study staff. Keep applying study medication to the same facial and neck areas throughout the study, even if the color is returning in these areas.
3. You will want the tip of your applicator to be saturated but not too much as to cause dripping. An applicator should only be dipped in the bottle once and then discarded. You may use more than one applicator per session as needed to ensure all areas of your face and if applicable, your neck designated by the study staff for treatment have medication applied.
4. Keep the study medication out of your eyes. If the study medication gets in your eyes, rinse the area well with water for up to 15 minutes. Contact the study doctor for further advice on managing the eye exposure.
5. You will apply study medication twice a day, approximately 8 to 12 hours apart. Once you apply study medication, do not wash your face or neck (If applicable) for at least 6 hours.
6. Remember to bring your study medication bottles, both used and unused, to each study visit.
7. Avoid exposing your face and neck (if applicable) to excessive natural or artificial ultraviolet radiation (e.g., sunlight, tanning beds) and use sunscreen on the face and neck (if applicable), if excessive sun exposure cannot be avoided.
8. Remove any products applied to the face and neck (if applicable) at least 1 hour before study visits. Do not apply study medication less than 6 hours before a study visit. If your visit is in the morning you should wait until after the visit to apply your study medication.
9. Open one bottle of study medication at a time. Each bottle of study medication should be used for 60 days only, even if there is remaining study medication.

Preparation for Study Medication Application

1. Gather a washcloth or towel, the study medication bottle, disposable applicators and a mirror.
2. Wash your hands with soap and water before and after using this study medication.
3. Gently wash your face and if applicable, your neck, ensuring all facial and neck areas are clean. Use your normal cleansing regime as approved by your study doctor. Do not use abrasive cleansers or materials on your face and if applicable, your neck.

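### The planned summaries of the 0–3 local tolerability grades cannot show how many subjects ever had a moderate or severe reaction; add per-grade counts and worst grade per subject

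*Combined protocol and SAP*

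**What the plan says.** Section 8.2.5 has the investigator grade signs and the subject grade symptoms. Each rater "should report the one integer that best describes the average overall severity on the treatment areas of the face using the scales below", and every scale runs from 0 (clear) to 3 (severe). On timing: "At Visits 2-11, the investigator and the subject will evaluate the LTA signs and the LTA symptoms respectively". Visit 2 has readings before and after the first application.

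Two planned summaries reach these grades:

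- The general rule in Section 11.2: "Summary descriptive statistics (N, mean, median, SD) by visit will be provided for all safety and efficacy parameters".
- The specific one, also in Section 11.2: "Change from baseline in the Local Tolerability Assessments (LTA) to end of treatment (Visit 10) will be summarized". The synopsis says the same and names Visit 2 as baseline: "Change from baseline (Visit 2) in the Local Tolerability Assessments (LTA) to end of treatment (Visit 10) will be summarized".

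No section plans a count of subjects at each grade, a shift table, or a worst post-baseline grade per subject. Section 11.2 also tabulates the proportion of subjects with treatment-emergent adverse events by System Organ Class. Section 4.1 makes tolerability part of the primary objective.

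**The concern.** The basic tolerability question for a topical product is how many subjects had a moderate or severe reaction at any time. A change score at Week 24 does not see a reaction that came and went earlier. A by-visit mean blends the number of subjects affected with the severity of their reactions, and it carries no information on whether the same or different subjects are affected from one visit to the next. A study report built on the planned statistics could therefore describe quite different tolerability profiles in the same terms, on a component of the primary objective.

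**Working it through.** The documents give no tolerability rate and no figure to reproduce. The check compares what the planned statistics return with what a worst-grade table returns, on assumed data.

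**Inputs from the documents.** N = 33 (Section 11.1); integer grades 0–3 (Section 8.2.5); eight on-treatment visits after baseline, Visits 3–10 (Section 6.3).

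**Assumed.** All baseline grades are 0 and all 33 subjects are observed at every visit.

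**Formulas.** Mean = sum of grades / 33. SD = √[(sum of squares − (sum)²/33) / 32]. Exact (Clopper–Pearson) 95% limits for x of n are the 2.5% point of Beta(x, n−x+1) and the 97.5% point of Beta(x+1, n−x).

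**1. Same by-visit output, different subjects.**

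- Scenario A: one subject is at grade 3 at every one of Visits 3–10.
- Scenario B: eight different subjects are at grade 3 once each, one per visit.
- At each visit, in both scenarios, exactly one of 33 subjects is at grade 3. Mean = 3/33 = 0.09; SD = √[(9 − 9/33)/32] = 0.52; median = 0.
- Mean change to Visit 10 is 0.09 in both.
- Worst grade 3: A gives 1/33 = 3.0% (0.1% to 15.8%); B gives 8/33 = 24.2% (11.1% to 42.3%).

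By-visit statistics depend only on the distribution of grades at each visit, whereas the number ever affected depends on how grades link within subjects. With one of 33 affected at each of eight visits, that number can be anything from 1 to 8.

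**2. Short-lived reactions, none at Visit 10.** Seven subjects each have one grade 3 reaction, one per visit at Visits 3–9. Each of those visits shows mean 0.09, SD 0.52 and median 0, and the change to Visit 10 is 0.00. Worst grade gives 7/33 = 21.2% (9.0% to 38.9%).

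**3. Reactions clustered at one visit.** Eight subjects are at grade 2 at Visit 3 only. The Visit 3 mean is 16/33 = 0.48 and SD = √[(32 − 256/33)/32] = 0.87, so the signal shows in the mean. The median is still 0 and the change to Visit 10 is 0. With 33 subjects the median is the 17th ordered value, so it leaves 0 only when 17 are affected at the same visit.

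**The case against.** The strongest reply is that early reactions are not lost. Five of 33 subjects at grade 2 at Week 1 would print as a mean of 10/33 = 0.30 (SD 0.73) against a zero baseline. That is correct: for clustered reactions the planned statistics dilute rather than conceal. The reply does not reach staggered or isolated reactions.

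A second reply is that local reactions also appear as adverse events. Section 7.6 says: "If the subject experiences application site AE(s), study medication may be stopped for up to a total of 3 days". A reaction that leads to such a pause is thus already an adverse event and counts in a per-subject incidence. This stands as a partial backstop. It relies on the reaction being reported as an event, and that table is by System Organ Class, not by tolerability grade.

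Third, the wording in Section 11.2 does not forbid frequency tables, and this is a descriptive pilot with no decision rule resting on these grades. That limits the weight of the point, but the named statistics remain the ones the plan commits to.

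A reader might also infer three stronger criticisms, which the documents do not support:

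- *Subjects who stop for intolerance drop out of the summary.* Section 5.9 asks for every effort to obtain the Visit 10 assessments at early discontinuation, Visit 10 includes both tolerability ratings, and earlier grades stay in the by-visit summaries.
- *Visit means must sit near zero because of the Appendix 1 instruction* "Do not apply study medication less than 6 hours before a study visit". No data show this. The rule could bear on investigator-rated signs, but symptoms at Visits 3–11 cover the previous 24 hours and Visit 2 has post-dose ratings.
- *Laboratory tabulation is restricted to results judged clinically relevant.* Section 11.2 says "Vital signs and clinically relevant abnormal laboratory results will also be tabulated and presented", which comes on top of by-visit statistics for all safety parameters.

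**Conclusion.** The point holds as a weakness in the choice of summary. Mean, median and SD by visit with change to Visit 10 cannot give the number of subjects who ever had a moderate or severe local reaction. In the assumed scenarios, identical by-visit output is compatible with 3.0% or 24.2% of subjects reaching grade 3, and a zero change at Visit 10 is compatible with 21.2%. These figures illustrate what the statistics can miss; they do not predict reaction rates. They assume zero baseline grades and complete data in 33 subjects.

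The point does not mean that local reactions would go unreported: clustered reactions move the visit mean, and reported reactions reach the adverse event table. It is a worthwhile improvement to a descriptive pilot, serving one component of its primary objective.

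Worst grade has limits of its own. Ratings stop at Visit 11 although treatment runs up to 48 weeks, so Weeks 28–48 are not covered. Under Section 6.4.5, subjects who consent to continue at Visit 10 skip Visit 11, so their last rating is at Week 24. Reactions between visits are also missed, since symptoms use a 24-hour recall and visits are about four weeks apart after Visit 5.

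**What to change.** In Section 11.2, and to match in the synopsis:

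- For each graded sign and symptom, tabulate n (%) of subjects at each grade by visit.
- For each, tabulate n (%) of subjects by worst post-baseline on-treatment grade, with the Visit 2 post-dose grade shown separately. First settle which symptom rows apply: Section 8.2.5 lists stinging and burning, but gives scales for itching and for burning/stinging.
- Keep the change to Visit 10 as support, labelled Week 24 rather than end of treatment.
- State that ratings cover Visits 2–11 only, so worst grade does not describe Weeks 28–48 or reactions between visits.

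As a secondary addition, tabulate from central-laboratory values the number of subjects crossing each limit in Table 1 and Section 9.2.4.2, alongside the planned by-visit statistics and clinically relevant abnormalities.

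The cost is programming and a few more tables. No new data are needed and no clinical rule changes.
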